4 RATIONALE AND BACKGROUND

Pulmonary Arterial Hypertension (PAH) is a rare, progressive and life-threatening disease. It is characterized by a chronic increase in pulmonary vascular resistance (PVR), due to progressive vascular remodeling that can ultimately lead to right heart failure and death [1,2]. Symptoms of PAH are related to right heart failure and include exercise-induced dyspnea, exhaustion, leg edema and decreased quality of life. In untreated patients with idiopathic PAH, the life expectancy is reduced to 2.8 years after diagnosis, whereas in contemporary registries in the era of modern PAH-specific treatments the survival rates have increased to 83% and 58% at 1 and 3 years respectively [3,4]. The incidence is currently estimated as 2.4 cases per million adult inhabitants per year with a prevalence of 15 cases per million adult inhabitants [5]. Available PAH-specific treatments include prostacyclin analogues, endothelin receptor antagonists, and PDE5-inhibitors. The available drugs predominantly act as vasodilators and improve exercise capacity [6]. Despite advances in the clinical management based on these available therapies for PAH, there is still significant unmet medical need for improvement as the mortality of patients with PAH remains high (15% at 1 year and 32% at 3 years) [7].

Chronic Thromboembolic Pulmonary Hypertension (CTEPH) is a different progressive and life-threatening type of pulmonary hypertension. Whereas symptoms, as well as epidemiology, of CTEPH are similar compared with PAH, there are significant differences regarding etiology, diagnosis and treatment [8,9]. In CTEPH the increase in pulmonary vascular resistance is a result of a pulmonary artery obstruction by residual organized thrombi [10]. A ventilation-perfusion scan is important for differential diagnosis as a normal scan excludes CTEPH [11]. The standard and potentially curative treatment for CTEPH is pulmonary endarterectomy (PEA). However, 20 to 40% of patients are not eligible for surgery and in 10-15% of patients PH may persist or reoccur after surgery [12-15]. Specific PAH drugs had failed in the past to show efficacy in inoperable CTEPH and before Adempas[®] no drug treatment has been approved for these patients [16].

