6 RESEARCH METHODS

6.1 Study Design

This registry is a national, multicenter, prospective, single-arm study of patients who will be treated with commercial riociguat for the locally approved indications of PH. The study will start after Adempas[®] has been authorized and made commercially available in China.

All patients prescribed with Adempas[®] for a medically appropriate use, consent to participate, and fulfill the selection criteria are eligible for enrollment into the study. Once enrolled, all aspects of the study will be conducted in an observational manner with no additional visits, procedures, etc. required as part of the study. All decisions on clinical management of the patient, including the actual treatment duration will be determined solely by the physician.

Patients will be followed up for an observation period of at least 1 year or until 30 days after end of Adempas[®] therapy. The enrollment period to obtain the required 80 patients is expected to be up to 14 months. Patient's clinical information will be documented at time of the initial visit and approximately every three to six months according to routine clinical practice thereafter. Data collection will continue until 30 days after the end of Adempas[®] therapy. Serious adverse events will be followed up until resolution.

Considering the difficulty of affordability of local patients during the study, sponsor will provide drug with no charge once medical decision on the prescription is made by physician and patients signed the informed consent. The free drug will be provided from the date of the first patient in to one year after the last patient in.

6.1.1 **Primary Endpoint(s)**

The primary endpoints are:

- Incidence of adverse events/serious adverse events
- Incidence of all-cause mortality

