6.2.8 Visits

The study protocol does not define exact timing of the follow-up visits. The clinical information will be collected, if available and done as per standard of care.

The investigator will document an initial visit, follow-up visits and a final visit for each patient in the case report form (CRF). Follow-up visits in clinical practice usually take place every 3 to 6 months. The CRF will allow for the documentation of visits as performed according to the management of the individual patient.

The final visit is meant to document the end of observation.

Patients will be followed up for an observation period for around 1 year or until end of study (until the last subject has been followed for 1 year) or until 30 days after end of Adempas[®] treatment. The enrollment period to obtain the required 80 patients is expected to be up to 14 months, therefore the study period from FPE to LPLV will be ~26 months.

Enrollment/Initial Visit

Once a patient is found eligible for inclusion, the investigator will inform the patient about the study. This will include discussing the consent form and asking the patient to read and – when agreeing to participate – sign the informed consent.

For patients in Bayer studies PATENT 2 and CHEST 2, their eligibility for EXPERT-China study will be evaluated after the completion of the Termination Visit and the Safety Follow-up Visit 30 days later in BAY 11349/12935.

The following information will be collected (details in Section 6.3):

- Patient demographics
- Medical history
- Comorbidity
- Adverse events
- PH etiology according to Nice Classification 2013 and disease history
- Pregnancy status
- History of smoking
- 6-minute walking distance*
- WHO FC*
- Borg dyspnea index*
- EQ5D VAS*
- Lung function*, Cardiac rhythm
- Hemodynamic parameters from right heart catheter measurement*
- Biomarkers (NT-proBNP, BNP) *
- Laboratory tests*
- Systemic BP before start of Adempas[®]
- Treatment:
 - o Relevant prior and concomitant medication
 - o PAH-specific drugs or Adempas®
- Resource use

*if available and done as per standard of care

Follow-up Visits During Treatment

Follow-up examinations in clinical routine usually take place every 3 to 6 months. The CRF will allow for visits to be documented according to the management of the individual patient. At each of these visits the following will be documented:

- Adverse events
- Changes of treatment
- Changes regarding demographics, pregnancy, smoking

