6.7.3 Analysis of Primary Outcome(s)

The main goal of this national registry is to assess the long-term safety of Adempas[®] in real life clinical use. Incidences of treatment-emergent adverse events, serious adverse events and all-cause mortality will be calculated, including adverse events of interest. An adverse event is considered as treatment-emergent when it has started or worsened after first dose of study medication after enrollment up to 2 days after end of treatment with study medication.

For the events, the 'raw' incidence proportion (regardless of the time each patient is treated), i.e. number of patients with events divided by the number of treated patients, will be presented as well as incidence rates, i.e. number of patients with events divided by the cumulative person-time on treatment (person-years) separately for incident and prevalent patients.

If the patient numbers allow, the statistics will be calculated for Adempas[®] and stratified for medically relevant subgroups, e.g.:

- Age
- Gender

MK-4836-001-01 FINAL PROTOCOL

- Aetiology (Nice Classification of PH)
- Hepatic impairment at baseline
- Renal impairment at baseline
- WHO functional class group at baseline
- According to e.g. 6 MWD thresholds \geq 380 m versus < 380 m at baseline
- Type of PH pre-treatment
- Concomitant medication use
- Systolic blood pressure at baseline
- Dosing level

A comprehensive list of medically relevant subgroups will be added to the SAP.

Tables which show the incidence proportion of adverse events overall and by MedDRA preferred term within the primary SOC will also be presented. Incidences of adverse events and serious adverse events starting more than 2 days after end of treatment will be tabulated separately.

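### The primary incidence measures in Section 6.7.3 have no time horizon although follow-up length depends on enrolment date, and the person-year rate as defined does not fully correct this for non-fatal events

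*Protocol*

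**What the plan says.** Section 6.1.1 names the primary endpoints as "Incidence of adverse events/serious adverse events" and "Incidence of all-cause mortality", with no time point for either.

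Section 6.7.3 gives two summaries. One is "the 'raw' incidence proportion (regardless of the time each patient is treated"), which puts patients having an event over everyone treated. The same sentence adds that this "will be presented as well as incidence rates, i.e. number of patients with events divided by the cumulative person-time on treatment (person-years"). These rates are to be given apart for incident and for prevalent patients. A later paragraph says: "Tables which show the incidence proportion of adverse events overall and by MedDRA preferred term within the primary SOC will also be presented". For those tables only the proportion is named. Adverse events count as treatment-emergent up to 2 days after the end of treatment.

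Follow-up is described in several ways:

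- Section 6.1 sets a minimum of 1 year, or until 30 days after therapy ends. Free drug is supplied until one year after the last patient enters.
- The Abstract and Section 6.5 speak of around 1 year.
- Section 6.2.8 offers three end points: about a year, "until end of study (until the last subject has been followed for 1 year"), and 30 days past the end of treatment. It gives up to 14 months of enrolment and a study period of about 26 months.
- The final-visit text in Section 6.2.8 places the last visit at the earlier of 30 days after discontinuation and the end of the study.

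**The concern.** A count of patients with at least one event, divided by all treated patients, is a risk only if everyone is observed for the same stated period or if censoring is handled. Here the observation period is set by enrolment date for patients who stay on drug and by the stopping date for those who do not. Two groups with the same underlying risk can show different proportions because one enrolled earlier. A reader given the final percentage for deaths or SAEs could not say over what period it applies.

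A person-year rate is the usual companion for unequal exposure. As worded, however, its denominator is all person-time on treatment, while its numerator counts each patient once. Time after a first non-fatal event adds to the denominator but can add nothing to the numerator. The rate therefore has its own dependence on follow-up, in the opposite direction to the proportion.

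**Working it through.** **Range of follow-up.** Enrolment of 14 months plus 12 months for the last patient gives 14 + 12 = 26 months, which reproduces the study period in Section 6.2.8. A patient who stays on therapy to the end of the study is observed for T = 12 (last enrolled) to 26 months (first enrolled). With uniform enrolment the mean is (12 + 26)/2 = 19 months.

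**Assumptions.** Uniform accrual, constant hazard, no early discontinuation. The 1-year and 3-year mortality figures come from Section 4 ("the mortality of patients with PAH remains high (15% at 1 year and 32% at 3 years")) and serve only as plausible inputs. The 50% 1-year AE risk is assumed, not taken from the protocol.

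**Mortality, constant hazard.**

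- h = −ln(1 − 0.15) = 0.1625 per year.
- Risk at T = 26 months: 1 − exp(−0.1625 × 26/12) = 29.7%.
- Expected raw proportion with T uniform from a to b years: 1 − [exp(−ha) − exp(−hb)] / [h(b − a)].
- All patients (a = 1, b = 26/12): 1 − (0.850 − 0.703)/(0.1625 × 1.167) = 22.6%, or about 18.1 of 80, against 12 of 80 at 12 months.
- First-enrolled half (19 to 26 months): 26.2%. Second half (12 to 19 months): 18.9%. The hazard is identical in both.
- Non-uniform enrolment: 24.6% if half enrol in the first 3 months, 20.4% if half enrol in the last 3.

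**Mortality, hazard fitted to both Section 4 figures.** A constant hazard from 15% at 1 year implies 1 − 0.85³ = 39% at 3 years, not 32%. With 0.1625 in year 1 and −ln(0.68/0.85)/2 = 0.1116 afterwards, the raw proportion is 20.3% (16.2 of 80), and 25.4% for a patient observed for 26 months.

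**Non-fatal event, 50% 1-year risk.** h = −ln(0.5) = 0.693 per year.

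| Enrolled | Mean follow-up | Raw proportion | Rate as defined |
|---|---|---|---|
| First half | 22.5 months = 1.875 y | 73% | 0.726/1.875 = 0.39 per year |
| Second half | 15.5 months = 1.292 y | 59% | 0.589/1.292 = 0.46 per year |
| All | 19 months = 1.583 y | 66% | 0.657/1.583 = 0.42 per year |

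With exactly 12 months for everyone, the rate as defined would be 0.50/1 = 0.50. At the same true hazard, early enrollees look worse on the proportion and better on the rate. With person-time stopped at the first event, the expected ratio is 0.693 in every row.

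For death this flaw does not arise, because treatment time ends at death. The mortality rate still averages over unequal follow-up and does not give the share of patients dead by a stated time.

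**The case against.** The strongest reply is that the protocol is open about this. It labels the proportion as ignoring time, pairs it in the same sentence with person-year rates reported separately for incident and prevalent patients, and calculates treatment duration for each patient (Section 6.7.2). The analysis is descriptive, and Section 6.7.1 leaves statistical detail and table content to the SAP, which is not at hand. Much of this stands. The proportion is neither the only nor the designated primary summary, and the absence of a Kaplan-Meier estimate from the protocol is not in itself an error. What remains is what the protocol does fix: a proportion without a horizon, and a rate whose stated denominator does not repair it for non-fatal events.

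Several stronger readings are tempting but not supported:

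- *That the registry's mortality will be misjudged against 15% and 32%.* No such comparison is planned. The figures are background for PAH, the title of the cited source refers to survival from diagnosis, and Section 6.9 expects mostly prevalent PAH and CTEPH cases.
- *That every patient is covered for months 0 to 12.* Observation ends 30 days after stopping if that comes first.
- *That the spread to 26 months is certain.* Around 1 year could mean about 12 months for all. That reading would leave the end-of-study clause with little purpose, but the text permits it.
- *That the incident and prevalent results will be distorted.* This would require the groups to enrol at different times, and the protocol gives no enrolment order.
- *That the headline and SOC/preferred-term tables should be cut at 12 months.* With a mean of 19 months this would move (19 − 12)/19 = 37% of planned observation out of the main tables of a study whose objective is long-term safety.

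**Conclusion.** The point holds in limited form. The primary incidence measures have no defined time horizon, and the companion rate does not fully correct for unequal follow-up in non-fatal events. If the end-of-study rule applies, the proportion exceeds the 12-month risk by roughly 5 to 8 percentage points at a 1-year mortality of 15%, and it varies by about 4 points with enrolment pattern alone under constant hazard. These sizes assume no early discontinuation. Stopping shortens follow-up and would reduce the excess, but it makes the period behind the percentage less definite still. If everyone is in fact followed for about 12 months, the spread due to enrolment date largely disappears and only variation from stopping remains. The plan should be improved on this point; it does not invalidate the study.

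**What to change.** Keep the planned proportions, rates and full-follow-up AE tables. In Section 6.7.3:

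- Add a 12-month Kaplan-Meier estimate of all-cause mortality.
- Add 12-month cumulative incidences of first SAE and first AE of interest, with death as a competing event.
- Give each with a 95% CI and numbers at risk, overall and by incident/prevalent group.
- For first-event rates, count person-time only up to the first event.

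In the Abstract and Sections 6.1, 6.2.8 and 6.5, reconcile the three descriptions of follow-up (at least 1 year, around 1 year, until end of study) into one rule.

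The cost is some wording and a few extra tables from data already collected. Intervals will be wide: with 80 patients and a 15% risk the approximate half-width is 1.96 × √(0.15 × 0.85/80) = 7.8 percentage points before any censoring, and it will be wider within the incident and prevalent groups.

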6.7.2 Analysis of Treatment Data

Duration and dose of the Adempas[®] treatment during the observation period will be calculated for each patient. The dose will be displayed at the different visits/time windows. The number of patients adding and removing various PH medications (including Adempas[®]) will be summarized using frequency tables.

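### The incidence rate in Protocol 6.7.3 counts each patient once but keeps time after the first event in the denominator, so for common non-fatal events it falls below a first-event rate and depends on length of follow-up

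*Protocol*

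**What the plan says.** Section 6.1.1 of the Protocol lists "Incidence of adverse events/serious adverse events" as a primary endpoint, together with all-cause mortality. Section 6.7.3 sets the scope of the calculation: "Incidences of treatment-emergent adverse events, serious adverse events and all-cause mortality will be calculated, including adverse events of interest".

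That section then fixes two measures. The first is a raw proportion: "number of patients with events divided by the number of treated patients, will be presented as well as incidence rates". The second is the rate, spelled out as "number of patients with events divided by the cumulative person-time on treatment (person-years) separately for incident and prevalent patients". Section 6.7.4 says the secondary safety outcomes are handled in a similar way.

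Nothing in sections 6.7.1 to 6.7.5 ends a patient's person-time at the first event. Section 6.7.2 states that the duration and dose of Adempas "treatment during the observation period will be calculated for each patient", which is whole treatment time within observation.

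On follow-up, section 6.1 says: "Patients will be followed up for an observation period of at least 1 year or until 30 days after end of" Adempas therapy. Section 6.2.8 lets follow-up run until the last patient has completed 1 year. On enrolment it says: "The enrollment period to obtain the required 80 patients is expected to be up to 14 months", and "therefore the study period from FPE to LPLV will be ~26 months".

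**The concern.** A rate needs a numerator and a denominator that match. If the numerator is patients with a first event, the denominator should be time at risk of a first event. If the denominator is all treatment time, the numerator should be all events. Section 6.7.3 pairs the numerator of the first with the denominator of the second.

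After a first non-fatal event, a patient who stays on treatment adds person-time and can add nothing to the count. The figure therefore cannot exceed 1 divided by the treatment time, whatever the hazard. It also falls as follow-up lengthens, even when the hazard is constant.

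The rate is there to adjust for unequal exposure, since 6.7.3 itself says the proportion ignores how long each patient was treated. For common events the rate as defined does not achieve that adjustment. Groups with the same hazard but different treatment times would show different rates, and 6.7.3 plans rates by incident and prevalent status and, where numbers allow, by many subgroups.

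**Working it through.** **Plan's own figure.** The protocol states no AE rate, so there is none to reproduce. The follow-up range does reproduce: 14 months of enrolment + 12 months = 26 months from first patient enrolled to last visit.

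**Inputs from the protocol.** N = 80 (6.2.8, 6.5). Treatment time T is 1 year (6.1) up to 26/12 = 2.17 years (6.2.8). One-year PAH mortality is 15% (section 4).

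**Assumptions.** The 1-year risk p of a first event runs from 5% to 90%. The hazard is constant, λ = −ln(1 − p). All patients stay on treatment throughout, including after the event.

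**Formulas.**
- Rate as written: (1 − exp(−λT)) / T
- First-event rate, with time stopped at the event: λ
- Ratio: (1 − exp(−λT)) / (λT), which is below 1 for any λT > 0

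**Worked case, p = 50%, T = 1.** λ = −ln(0.5) = 0.693. Expected patients with an event: 80 × 0.5 = 40. Person-time as written: 80.0 years, giving 40/80.0 = 0.500. Person-time at risk: 40/0.693 = 57.7 years, giving 0.693. Ratio 0.721, so the rate is 27.9% low.

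**Range.** Each cell gives the rate as written, per person-year, and its shortfall against λ.

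| 1-year risk | λ | T = 1 year | T uniform over 12–26 months | T = 26 months for all |
|---|---|---|---|---|
| 5% | 0.051 | 0.050 (2.5%) | 0.049 (4.1%) | 0.049 (5.4%) |
| 10% | 0.105 | 0.100 (5.1%) | 0.097 (8.2%) | 0.094 (10.6%) |
| 30% | 0.357 | 0.300 (15.9%) | 0.270 (24.3%) | 0.248 (30.3%) |
| 50% | 0.693 | 0.500 (27.9%) | 0.415 (40.1%) | 0.359 (48.2%) |
| 70% | 1.204 | 0.700 (41.9%) | 0.530 (56.0%) | 0.428 (64.5%) |
| 90% | 2.303 | 0.900 (60.9%) | 0.610 (73.5%) | 0.458 (80.1%) |

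The last column is a ceiling, because only the earliest enrolees could be followed for 26 months.

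**Dependence on follow-up.** In the 70% row the hazard is the same throughout, yet the rate is 0.700 at 1 year and 0.428 at 26 months. The second is lower by 1 − 0.428/0.700 = 39%.

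**Early clustering (a further assumption).** Suppose all events fall evenly in the first 8 weeks and T = 1 year. At-risk time per patient is (1 − p) + p × (8/52)/2.
- At p = 50% this is 0.538 years. The at-risk rate is 0.5/0.538 = 0.929 against 0.500 as written, 46% low.
- At p = 90% it is 0.169 years, and the rate as written is 83% low.

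**Mortality.** Death ends treatment time, so no time after the event can enter the denominator. At 15% in 1 year, λ = −ln(0.85) = 0.163 per person-year under either definition.

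**The case against.** The strongest reply is that the rate is one of two planned measures. The proportion is reported beside it, the tables by MedDRA preferred term are specified as proportions, and the proportion does not have this fault. That stands. A reader might infer that the primary endpoint as a whole is understated. The protocol does not support this, because neither the proportion nor all-cause mortality is affected.

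Second, patients with an event per unit of total exposure is a known summary, and the protocol states its formula openly. It is low only relative to a first-event rate. That also stands, but the protocol calls the quantity an incidence rate, which invites the first-event reading.

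Third, section 6.7.1 leaves calculated variables to the SAP, which is not available here. This stands only in part. The formula is already fixed in 6.7.3, and an SAP that stopped time at the first event would depart from it.

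Fourth, the sizes depend on assumed hazards, and several places in the protocol describe observation of around 1 year. That is fair. If observation in fact ends near 1 year for most patients, the 1-year column applies and dependence on enrolment date largely disappears, but the 1-year shortfall remains.

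A reader might also infer that incident and prevalent patients will be distorted by different amounts. The protocol does not show this. Nothing in it says that either group enrols earlier, stays on treatment longer or has more frequent events, and no formal comparison between them is planned.

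**Conclusion.** Wrong as written; should-fix. Followed literally, section 6.7.3 yields a figure that understates the first-event rate of common non-fatal AEs and SAEs and declines with longer treatment. Under constant hazards and 1 year on treatment, the understatement is negligible at low risk, over a quarter at a 1-year risk of 50%, and about three fifths at 90%. Follow-up beyond 1 year makes it larger.

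These sizes assume event risks that the protocol does not give, and patients who remain on treatment after the event. Where an event ends treatment, little or no later time accrues and the shortfall shrinks.

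A must-fix rating is not warranted. The analysis is descriptive, no test or decision threshold depends on the rate, and a sound proportion accompanies it.

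**What to change.** In section 6.7.3, define the incidence rate as patients with a first event of the type analysed divided by person-time at risk. Count that time from the first dose after enrolment to the first such event or, if there is none, to the end of the treatment-emergent window (end of treatment + 2 days). For AEs that can recur, also report all events over total on-treatment person-years, labelled as an event rate. Carry the same definitions into the SAP and the secondary safety outcomes.

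No new data are needed, because AE onset and treatment dates are already required to decide whether an event is treatment-emergent. The cost is a short protocol change and a little more programming, since person-time must be computed separately for each event type. Reported rates of common AEs will be somewhat higher than under the present formula; the proportions and mortality figures will not change.
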